## 1.2. Compound Background

GED-0301 inhibits the expression of Smad7, a key regulatory modulator of TGF- $\beta$ 1, by targeting a sequence in Smad7 messenger ribonucleic acid (mRNA) (Boirivant, 2006). There is a marked overexpression of Smad7 in the inflamed intestine of patients with IBD, such as CD and UC (Monteleone, 2001). This is associated with a reduction in p-Smad3, a crucial step in TGF- $\beta$ 1-mediated signal transduction. By blocking TGF- $\beta$ 1 activity, high Smad7 levels contribute to sustained production of proinflammatory molecules (such as IFN- $\gamma$  and TNF- $\alpha$ ) in IBD-affected tissues. The identification of the role of Smad7 in IBD provided the rationale for the development of mongersen (GED-0301).

GED-0301 is an investigational medicinal product in clinical development for the treatment of CD and ulcerative colitis (UC). GED-0301 is an antisense oligodeoxynucleotide (21-mer) that is complementary to the sequence of the messenger ribonucleic acid (mRNA) transcript of Smad7. It has a phosphorothioate backbone. It may be described chemically as the fully neutralized sodium salt of a 3'  $\rightarrow$  5' linked 2'-deoxyribosephosphorothioate oligonucleotide 21-mer in which each of the 20 internucleotide linkages is an O,O-linked phosphorothioate. Orally administered GED-0301 is formulated as a gastro-resistant delayed release pH-dependent tablet designed to deliver the active substance in the distal GI tract with negligible systemic exposure.

Although the etiology of CD has not been completely elucidated, there has been significant advancement in the understanding of the disease pathogenesis. There is evidence that the chronic intestinal inflammation is caused by an excessive immune response to mucosal antigens that is not appropriately controlled by the normal counter-regulatory mechanisms. One of the counter-regulatory mechanisms involves transforming growth factor- $\beta$ 1 (TGF- $\beta$ 1). TGF- $\beta$ 1 is a multifunctional factor that has been shown to be involved in regulating growth, differentiation, and function of immune and nonimmune cells (Monteleone, 2001). TGF- $\beta$ 1 has been shown to play an important role in the control of immune homeostasis and acts as a potent negative regulator of mucosal inflammation. TGF- $\beta$ 1 knockout mice developed a severe multiple-organ inflammatory disease, in which the lymphocytic infiltration of the affected organs was associated with increased production of TNF- $\alpha$  and interferon-gamma (IFN- $\gamma$ ). Studies have shown that abrogation of TGF- $\beta$ 1 signaling in T cells alone is sufficient to disrupt T and B cell homeostasis

and induce T cell-mediated inflammatory lesions in various organs, including the intestine. It has been widely demonstrated that neutralization of TGF- $\beta$ 1 results in the induction and/or amplification of pathogenic responses responsible for the development of experimental colitis resembling either CD or UC (Monteleone, 2012).

TGF- $\beta$ 1 signaling is regulated by Smads, a family of proteins that serve as substrates for TGF- $\beta$ 1 type I and type II receptors. The TGF- $\beta$  type I receptor recognizes Smad2 and Smad3 which, upon phosphorylation of Smad3, en route to the nucleus, associate with Smad4, forming complexes that participate in transcriptional control of target genes. In addition to the activating Smads, inhibiting Smad also exists. Smad7, on the other hand, interacts with activated receptors and prevents phosphorylation of Smad2 and Smad3. The advance in the understanding of the involvement of the TGF- $\beta$  signaling pathway in the pathogenesis of CD and the identification of the role of Smad7 in IBD has provided the rationale for the development of a new drug that, through the inhibition of Smad7 expression, could restore TGF- $\beta$ 1 signaling, thus inhibiting the production of pro-inflammatory molecules such as TNF- $\alpha$  and IFN- $\gamma$ .

### 1.2.1. Nonclinical Experience

Overall, GED-0301 exhibits an acceptable safety profile in preclinical species and the toxicology program for GED-0301 adequately supports the conduct of clinical studies.

Please refer to the Investigator's Brochure (IB) for information concerning the available preclinical, pharmacology, toxicology and drug metabolism studies of GED-0301.

### 1.2.2. Clinical Summary

#### 1.2.2.1. Clinical Pharmacology

The pharmacokinetics (PK) of GED-0301 were characterized in a Phase 1 first-in-human study in subjects with active CD. The systemic bioavailability of GED-0301 following oral administration at dose levels up to 160 mg/day for 7 days to human patients is negligible.

#### 1.2.2.2. Clinical Safety

Three clinical studies have been completed to date: [REDACTED], a Phase 1, dose-escalating, safety and PK study of 7 days of oral administration of GED-0301 in subjects with active CD, [REDACTED] a Phase 2 randomized, double-blind, placebo-controlled, dose-finding study of GED-0301 in subjects with active CD and [REDACTED], a Phase 2 randomized, double-blind, placebo-controlled, long-term extension study to evaluate the safety and tolerability of GED-0301 40 mg for the maintenance of CD in remission. [REDACTED]

[REDACTED] No deaths were reported during the conduct of the studies. No safety concerns that could modify the study conduct and/or investigational product (IP) administration arose from the studies.

Please refer to the IB for information concerning the available clinical studies and adverse event (AE) profile of GED-0301.

### 1.3. Rationale

#### 1.3.1. Study Rationale and Purpose

The purpose of this Phase 3 study is to demonstrate the efficacy and safety of GED-0301 in subjects with active CD to support its registration for the indication of the treatment of active CD. Active CD is defined as a CDAI score  $\geq 220$  and  $\leq 450$  at screening and a total Simple Endoscopic Score for Crohn's Disease (SES-CD)  $\geq 6$  at screening, or the ileum segmental SES-CD  $\geq 4$  at screening. Subjects must have failed or experienced intolerance to at least one of the following: budesonide; systemic corticosteroids; immunosuppressants (eg, azathioprine [AZA], 6-mercaptopurine [6-MP], or methotrexate [MTX]); or biologics (ie, infliximab, adalimumab, certolizumab or vedolizumab).

#### 1.3.2. Rationale for the Study Design

GED-0301-CD-002 is a double-blind, placebo-controlled study that will evaluate both short-term and long-term efficacy, as well as safety, of GED-0301 in subjects with active CD. Efficacy will be based on clinical activity, as measured by the Crohn's Disease Activity Index (CDAI) or average daily liquid or stool frequency and abdominal pain score, and endoscopic outcomes, as measured by the SES-CD. Crohn's Disease Activity Index, the current-standard for evaluation of clinical disease activity, is a validated, reproducible and responsive measure of CD that has been widely used in clinical trials for approximately 35 years.

The SES-CD is a validated endoscopic index that is considered the most suitable endoscopic outcome measure due to its ease of use and close correlation with the Crohn's Disease Endoscopic Index of Severity (CDEIS), considered the gold standard for endoscopic evaluation.

The primary efficacy measure will be clinical remission (defined as a CDAI score  $< 150$ ) during the Treatment Phase at Week 12. Key secondary efficacy measures will include: clinical remission at Week 52; endoscopic response-50 ([ER-50], defined as a reduction of at least 50% compared with baseline in SES-CD) at Week 52; clinical response (defined as a decrease from baseline in CDAI  $\geq 100$  points) at Week 12;

steroid-free clinical remission at Week 52; sustained clinical remission at both Week 12 and Week 52; endoscopic response-25 ([ER-25], defined as a reduction of at least 25% compared with baseline in SES-CD) at Week 12; and the evaluation of endoscopic remission (defined as SES-CD  $\leq 2$ ) at Week 52.

Laboratory evaluations, AEs, vital signs, electrocardiograms (ECGs), pregnancy tests and physical examinations will be monitored during the study to evaluate safety.

### 1.3.3. Rationale for Dose, Schedule and Regimen Selection

Three oral dose regimens of GED-0301 versus placebo are being evaluated for the treatment of subjects with active CD:

- GED-0301 160 mg QD for 12 weeks; followed by placebo QD for 4 weeks; followed by alternating GED-0301 160 mg QD for 4 weeks and placebo QD for 4 weeks, until the Week 52 Visit;
- GED-0301 160 mg QD for 12 weeks; followed by placebo QD for 4 weeks; followed by alternating GED-0301 40 mg QD for 4 weeks and placebo QD for 4 weeks, until the Week 52 Visit;
- GED-0301 160 mg QD for 12 weeks; followed by continuous GED-0301 40 mg QD, until the Week 52 Visit.

The doses and dose regimens for this study were selected based on pre-clinical data and clinical data from the Phase 1 study [REDACTED] and the Phase 2 dose-finding study [REDACTED] in subjects with active CD.

The key considerations for the selection of the appropriate dose and dosing regimens were:

1. the very low systemic exposure in animals without signs of toxicity when given orally in doses at least 10 times higher, by body weight, than the proposed GED-0301 160 mg QD dose in humans;
2. the negligible systemic exposure of GED-0301 in humans;
3. the demonstrated efficacy of GED-0301 in Phase 1 and Phase 2 studies;
4. the similar safety profile of the various GED-0301 dose treatment groups in Study [REDACTED]; comparable numbers and types of TEAEs across all treatment groups, including the placebo treatment group were observed, with few SAEs or AEs leading to discontinuation of IP.

Study [REDACTED] demonstrated GED-0301 40 mg QD and 160 mg QD to be efficacious and safe after 2 weeks of treatment in subjects with steroid dependent or refractory CD.

Therefore, these data, in addition to the similar and favorable safety profiles of GED-0301 40 mg QD and 160 mg QD, provide supportive evidence for the selection of 160 mg QD as the initial dose of GED-0301 for a 12-week treatment induction of clinical remission and endoscopic response

[REDACTED]. The 12-week duration was selected in order to optimize therapeutic benefit, since it is expected that it would take a longer duration of treatment to achieve endoscopic benefit, such as endoscopic response, than to achieve clinical signs and symptoms benefit or clinical remission, in a moderate to severe CD population. Also, there is no consensus about the appropriate timing to assess the endoscopy evaluation, ranging from 10 to 26 weeks in different clinical studies

(Dave, 2012). In addition, endoscopic assessments at time points later than 12 weeks in placebo-controlled studies have posed the problem of limited comparative data due to the low number of placebo subjects remaining beyond the 12-week time point. Hence, the 12-week time point was selected for the endoscopic endpoint in this study.

Three active dosing regimens will be evaluated following the initial 12-week treatment with GED-0301 160 mg QD, in which two different doses (160 mg QD and 40 mg QD) and different dosing schedules (continuous and alternating) will be evaluated in order to determine dose and dosing regimen that provides the best benefit to risk for subjects with active CD.

Two doses, 160 mg QD and 40 mg QD, were selected to be evaluated after the initial 160 mg QD 12-week treatment since the 160 mg QD dose is expected to provide the highest level of efficacy, and the 40 mg QD dose is the lowest efficacious dose, which has been demonstrated in subjects with active CD [REDACTED]. This is clinically pertinent, since subjects who achieve clinical response or clinical remission after the initial 12-week treatment may require a lower dose than that initially needed for the treatment of moderate to severe CD.

Three different dosing regimens will be evaluated: one continuous dosing regimen (GED-0301 40 mg QD) and two alternating dosing regimens (GED-0301 40 mg QD for 4 weeks on/4 weeks off and GED-0301 160 mg QD for 4 weeks on/4 weeks off). Consequently, these 3 different dosing regimen strategies correspond to incremental increases of 2-fold differences between each of the 3 arms in total IP exposure during the 40-week long-term maintenance treatment. The alternating dosing regimen is supported by findings from Study [REDACTED], in which after 2 weeks of dosing, the majority of subjects had a prolonged clinical improvement up to Week 12, suggesting that patients may not need continuous dosing. This strategy may be more advantageous for longer term treatment in patients with CD, including the potential for a more favorable benefit to risk profile than a continuous dosing regimen.

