## 2. STUDY OBJECTIVES AND ENDPOINTS

**Table 1: Study Objectives**

|   |
|---|
| Primary Objective  |
| The primary objective of the study is to evaluate the efficacy of GED-0301 compared with placebo on clinical activity at Week 12 in subjects with active Crohn’s disease (CD).  |
| Secondary Objectives   |
| The secondary objectives are: 
 
• To evaluate the efficacy of GED-0301 compared with placebo on endoscopic outcomes in subjects with active CD;
 
• To evaluate the long-term efficacy of GED-0301 compared with placebo on clinical activity in subjects with active CD;
 
• To evaluate the efficacy of GED-0301 compared with placebo on corticosteroid-free clinical remission in subjects with active CD;
 
• To evaluate the safety and tolerability of GED-0301 in subjects with active CD.
 
 |
| [REDACTED]  |
| [REDACTED]  |
| [REDACTED]  |
| [REDACTED]  |
| [REDACTED]  |
| [REDACTED]  |

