### 3. OVERALL STUDY DESIGN

#### 3.1. Study Design

This is a Phase 3, randomized, double-blind, placebo-controlled, multicenter study to evaluate the efficacy and safety of 3 treatment regimens of oral GED-0301 versus placebo in subjects with active CD (defined by a CDAI score  $\geq 220$  and  $\leq 450$  and a total SES-CD  $\geq 6$  at screening, or the ileum segmental SES-CD  $\geq 4$  at screening). Approximately 1064 subjects will be randomized in a 1:1:1:1 ratio (266 subjects per GED-0301 arm [total 798]; 266 subjects in the placebo arm) to receive 1 of 3 double-blind, oral GED-0301 treatment regimens, or identically appearing placebo once daily (QD) for 52 weeks. The total number of subjects with a total SES-CD score  $\geq 6$  is targeted to comprise approximately 80% of the study population.

Treatment assignment at baseline (Week 0/ Visit 2) will be stratified via an Interactive Web Response System (IWRS) based on concomitant use of corticosteroids (yes/no); concomitant use of immunosuppressants (eg, azathioprine [AZA], 6-mercaptopurine [6-MP], or methotrexate [MTX]) (yes/no), and previous exposure to biologics (ie, infliximab, adalimumab, certolizumab or vedolizumab) (yes/no). The total number of subjects with previous exposure to biologics is targeted to comprise approximately 35% of the study population.

Subjects will receive double-blind, oral GED-0301 or identically appearing placebo QD as follows (Table 4):

- GED-0301 160 mg QD for 12 weeks; followed by placebo QD for 4 weeks; followed by alternating GED-0301 160 mg QD for 4 weeks and placebo QD for 4 weeks, until the Week 52 Visit;
- GED-0301 160 mg QD for 12 weeks; followed by placebo QD for 4 weeks; followed by alternating GED-0301 40 mg QD for 4 weeks and placebo QD for 4 weeks, until the Week 52 Visit;
- GED-0301 160 mg QD for 12 weeks; followed by continuous GED-0301 40 mg QD, until the Week 52 Visit;
- Placebo QD until the Week 52 Visit.

Subjects who complete the GED-0301-CD-002 study at the Week 52 Visit may enter the Long-term Active-treatment Study (GED-0301-CD-004). Subjects who meet the criteria for early escape beginning at the Week 12 Visit and thereafter until the Week 52 Visit, may (a) continue in the study at the discretion of the Investigator based on the totality of clinical data, (b) enter the Long-term Active-treatment Study (GED-0301-CD-004), or (c) discontinue the study.

The criteria for early escape are defined as

(Table 7).

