### 9.3. Sample Size and Power Considerations

With a total of approximately 1064 subjects and a randomization ratio of 1:1:1:1, this study will randomize approximately 266 subjects into each of the three GED-0301 treatment groups and the placebo group. For the efficacy analyses of the first 12 weeks of the study, the three GED-0301 treatment groups will be pooled, due to the same treatment of GED-0301 160 mg QD received during the first 12 weeks, and the treatment comparisons will be made between GED-0301 160 mg QD (approximately 798 subjects) and placebo. For the efficacy analyses beyond Week 12, the treatment comparisons will be made between each of the three GED-0301 treatment groups and placebo. The study sample size is driven by the comparison of each of the three GED-0301 treatment groups with placebo with respect to the proportion of subjects with ER-50 at Week 52. The sample size and power calculations (not accounting for multiplicity adjustment) at a 2-sided significance level of 0.05 are given in [Table 5](#).

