#### 9.6. Efficacy Analysis

For the efficacy analyses of the first 12 weeks of the study, the three GED-0301 treatment groups will be pooled, due to the same treatment of GED-0301 160 mg QD received during the first 12 weeks, and the treatment comparisons will be made between GED-0301 160 mg QD and placebo. For the efficacy analyses beyond Week 12, the treatment comparisons will be made between each of the three GED-0301 treatment groups and placebo.

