## 11. EFFICACY ANALYSIS

All efficacy analysis tables will be presented by GED-0301 treatment regimen, placebo, and a total group combining all 3 GED-0301 treatment regimens. The 3 GED-0301 treatment regimens will be labeled as GED 160/GED 160 4 WK ALT, GED 160/GED 40 4 WK ALT, and GED 160/GED 40, and the total group combining all 3 GED-0301 treatment regimens will be labeled as GED Total. Formal treatment comparisons will be made between GED Total (ie, GED 160) and placebo for the efficacy analyses of the first 12 weeks, and between each of the 3 GED-0301 treatment regimens and placebo for the efficacy analyses beyond Week 12.

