## 11.4. Analyses of Secondary Efficacy Endpoints

### 11.4.1. Primary Analyses of Secondary Efficacy Endpoints

The primary analysis of each secondary efficacy endpoint will be performed similarly to the primary analysis of the primary endpoint. The treatment comparisons will be made between GED 160 (combining all 3 GED-0301 treatment regimens) and placebo for the endpoints at Weeks 4 and 12 and between each of the 3 GED-0301 treatment regimens and placebo for the endpoints at Week 52.

The analysis of the proportion of subjects who achieve corticosteroid-free clinical remission at Week 52 among subjects receiving oral corticosteroids at baseline will be based on the subjects included in the ITT population who receive oral corticosteroids for CD at baseline.

[REDACTED]

[REDACTED]

[REDACTED]

[REDACTED]

[REDACTED]

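### The regimens are meant to identify the best dose and schedule, but every visible comparison after Week 12 is against placebo, so the visible plan gives no between-regimen difference with a CI

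*Protocol*

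**What the plan says.** Protocol 1.3.3 gives the reason for carrying three active regimens past Week 12: they are evaluated "in order to determine dose and dosing regimen that provides the best benefit to risk for subjects with active CD". Table 4 shows that the active arms receive the same 160 mg dose for 12 weeks and then split into 160 mg alternating, 40 mg alternating and 40 mg continuous.

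The comparison rules that can be read are all against placebo:

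- Protocol 9.6: "For the efficacy analyses beyond Week 12, the treatment comparisons will be made between each of the three GED-0301 treatment groups and placebo". The Protocol Summary, Protocol 9.3 and SAP 4.4 say the same.
- SAP 11, on formal comparisons: "between each of the 3 GED-0301 treatment regimens and placebo for the efficacy analyses beyond Week 12".
- SAP 11.4.1, on secondary endpoints: "between each of the 3 GED-0301 treatment regimens and placebo for the endpoints at Week 52".

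The visible efficacy objectives have the same form, for example "To evaluate the long-term efficacy of GED-0301 compared with placebo on clinical activity in subjects with active CD" (Protocol Table 1). So does the sample size: "The study sample size is driven by the comparison of each of the three GED-0301 treatment groups with placebo" (Protocol 9.3). Table 5 gives power only against placebo and uses one assumed ER-50 rate for any active group.

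The SAP does report results by arm. Efficacy is presented by regimen (5.1), the visible analysis text in Section 11 gives each regimen a proportion, standard error and 95% CI, and all safety tables are by regimen (12).

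**The concern.** The three arms differ only after Week 12, so having three of them is useful mainly for comparing doses and schedules in that period. Table 4 supplies two clean contrasts: 160 mg against 40 mg on the same alternating schedule, and continuous against alternating dosing at the same 40 mg dose. The visible plan asks for neither.

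Without a planned difference, readers will tend to choose a regimen by asking which one reached p < 0.05 against placebo. That does not estimate a difference between regimens. SAP 11.1 has dropped multiplicity control, so three nominal p-values against placebo are what readers will see. Early termination makes the arms smaller and split results more likely, even if the regimens are equally effective.

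**Working it through.** **1. Reproduce the plan's power.** Two-group chi-square, pooled variance, two-sided 0.05, no continuity correction:

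power = Φ{ [d − 1.96·√(2p̄(1−p̄)/n)] / √[(p₁(1−p₁)+p₂(1−p₂))/n] }

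ER-50, 20% v 10%, n = 266 per arm: (0.100 − 0.0607)/0.0307 = 1.28, so power is 90.0% (Table 5: 90%). The same method gives 94.7% for Week 52 remission, 36% v 22% (Table 5: 95%), and 99.3% for Week 12 remission with 798 v 266 (Table 5: 99%). The method matches.

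**2. Regimen v regimen at planned size.** The documents give no between-regimen difference, so the differences below are assumptions. The lower regimen is set at the plan's active rate.

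| | ER-50 (20%) | Remission (36%) |
|---|---|---|
| 95% CI half-width, 1.96·√(2p(1−p)/266) | 6.8 points | 8.2 points |
| Power, 5-point difference | 28% | 22% |
| Power, 10-point difference | 76% | 65% |
| Difference with 80% power | 10.5 points | 12.0 points |
| Same, Bonferroni over 3 pairs | 12.3 points | 13.9 points |

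These figures take all 266 subjects per arm as evaluable, with missing data counted as nonresponse. The documents give no Week 52 numbers after termination. If 130 per arm were evaluable (an assumption), the half-widths would grow by √(266/130) = 1.43, to about 9.7 and 11.7 points.

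**3. Split significance when the regimens are equal.** Simulation of three active arms with the same true rate against one shared placebo arm. The table gives the chance that one or two of the three, but not all, reach p < 0.05 against placebo.

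| Evaluable per arm | ER-50, 20% v 10% | Remission, 36% v 22% |
|---|---|---|
| 266 | about 19 to 20% | about 12% |
| 130 (assumed) | about 48% | about 43% |

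**4. Illustration among Week 12 remitters.** Assumptions: 36% in remission at Week 12 (the plan's rate), so 0.36 × 266 ≈ 96 per active arm; 60% v 40% of these in remission at Week 52; the same Week 52 rate in Week 12 non-remitters in both arms. Overall Week 52 remission averaging 36% then needs (0.36 − 0.36×0.50)/0.64 ≈ 28% of Week 12 non-remitters to be in remission at Week 52.

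- Full arms, Week 52 remission: 0.36×0.60 + 0.64×0.28 = 39.6% v 0.36×0.40 + 0.64×0.28 = 32.4%. Power 41%.
- Full arms, sustained remission (Weeks 12 and 52): 0.36×0.60 = 21.6% v 0.36×0.40 = 14.4%. Power 58%.
- Week 12 remitters, 96 per arm: 60% v 40%. Power 80%; half-width 1.96·√(2×0.25/96) = 14.1 points.

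With a 15-point maintenance difference the three powers are 25%, 37% and 55%. With 10 points the subset power is only about 28%. If 10% rather than 28% of non-remitters reach remission at Week 52, the first figure (20-point case) rises from 41% to 49%.

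**5. Is Week 12 status a fair basis for a subset?** Protocol 6.2 places visit assessments before that day's dose, and Table 4 shows the regimens diverging only with product dispensed at Week 12. At the moment of selection the active arms are therefore exchangeable. This does not hold for active v placebo.

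**The case against.** The strongest reply is that the sentence in 1.3.3 is rationale. The visible efficacy objectives are against placebo, the stated purpose in 1.3.1 is registration, and the SAP was written after the trial had stopped. On that view further nominal contrasts with wide intervals are optional. This lowers the stakes but does not remove the mismatch between a stated aim and the visible analyses.

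Four more limits stand.

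- **Redaction.** Some objectives and endpoints are blacked out, as are parts of SAP 11. The protocol contents list a subgroup section (9.6.3) whose text is not in the public copy. A between-regimen or Week 12 subset analysis could be there. The claim covers visible text only.
- **Estimates are not wholly absent.** A reader can subtract two arm rates and combine their standard errors into a crude interval. What is missing is a prespecified, stratified difference and a rule for reading it.
- **Sustained remission.** This planned secondary endpoint already removes the dilution from late remission in Week 12 non-remitters, so 80% v 41% overstates the gain from the subset; 80% v 58% is the fairer comparison.
- **Randomization.** The SAP's Week 52 denominator (5.3.1, 11.2.2.1) keeps completers and those who left for reasons other than sponsor termination. Late enrollees thus count only if they left for another reason, and such departures may differ by regimen. Selection at Week 12 is sound; the Week 52 comparison may not fully preserve randomization.

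A reader might also infer that the trial cannot answer the regimen question with the data it collects. The documents do not support that: the regimens are concurrent, blinded, randomized arms ("Approximately 1064 subjects will be randomized in a 1:1:1:1 ratio"), and a between-regimen difference can be computed from data already planned.

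**Conclusion.** The point holds as a gap in the visible analysis plan. The aim in 1.3.3 is a choice among regimens, while every visible comparison rule after Week 12 is regimen against placebo, with no between-regimen difference, power statement or selection rule. The data could supply such differences, with the planned-size precision shown in step 2 of the working. That is enough to estimate and to detect large differences, but gives only 22 to 28% power for a 5-point difference, and less after early termination. The contrasts therefore belong in the SAP as estimates, not as powered tests. The gain from a Week 12 remitter subset is illustrative only: the 20-point effect, the 50% average maintenance rate and the 28% rate in non-remitters are assumptions that the documents do not give.

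**What to change.** In SAP 11 and 11.4.1, add two nominal, estimation-only contrasts at Week 52, each with a CMH-weighted stratified difference and 95% CI, for clinical remission, sustained remission and ER-50:

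1. Dose: GED 160/GED 160 4 WK ALT minus GED 160/GED 40 4 WK ALT.
2. Schedule: GED 160/GED 40 minus GED 160/GED 40 4 WK ALT.

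As a supportive analysis, repeat both in the active arms only, among subjects in remission and among subjects in clinical response at Week 12. Note there that the Week 52 denominator excludes subjects by reason for discontinuation and may not fully preserve randomization. State that differing significance against placebo will not be read as a difference between regimens.

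The cost is SAP wording and a few tables, with no new data and no change to conduct. The downside is wide intervals and nominal results. The contrasts address efficacy only; they do not supply a benefit-risk criterion, and the safety side would still rest on the by-regimen tables in SAP 12.
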